3.3 Data Sources/Data Collection Process

3.3.1 Data Sources

The data sources of this non-interventional observational study are Case Report Forms (CRFs) and patient questionnaires. Collection of data includes but not limited to subject demographics, clinical history, comorbidities, spontaneous adverse events, and concomitant medications. The following questionnaires will be utilized to collect data directly from participating subjects:

- HAQ DI
- SF-36
- EQ-5D-3L
- WPAI
- Patient Global Impression of Change (PGIC)
- Patient Treatment Satisfaction Questions
- HCRU

3.3.2 Data Collection

IMS will coordinate data collection with each site. At study initiation (Baseline, D0), patients will be asked to provide their written informed consent. After signing consent, the patients' questionnaires as recorded will be collected. At Week 12 and 24 time-points, the patients' questionnaires will be collected before them visiting their physicians. There will be a study coordinator or study nurse at each site to monitor the process. The study coordinator/nurse will collect the record of questionnaires directly. Physicians will not see the contents patients entered. The study coordinator/nurse will check to ensure all the forms are filled-in correctly.

In addition, physicians will also be asked to complete a clinical CRF in paper form based on the patient's medical records at baseline, 12 weeks, and 24 weeks. The CRF completed by physicians will be returned to the study coordinator/nurse at each site as well.

All data will be collected by the study coordinator/nurse at each site and returned directly to IMS. The data collection time is expected to be 10-13 months.

All patient and clinician data will be handled preserving confidentiality.

3.3.3 Ethics and Quality

Prior to any study-related data being collected, informed consent form will be reviewed, signed and dated by the patient and the person who administered the informed consent. A copy of the signed informed consent will be given to the patient and the original will be placed in the patient's medical record.

3.3.4 *Quality Assurance*

Prior to the initiation of the study, physician and site personnel will be trained on the study. Training will include a detailed discussion of the protocol, performance of study procedures, and completion of the CRFs and paper questionnaires.

All sites will be monitored during the course of study participation. One hundred percent (100%) source document review for safety will be performed.

All clinical data will be documented via the CRF. Study coordinators at each site will check the paper CRFs completed by the physicians and questionnaires completed by patients (e.g., all questions were answered). Data entry will be conducted by IMS. After entry of the data, computer logic checks will be run to check for inconsistent data. Any necessary corrections will be made to the database and documented via addenda, queries, and source data clarification forms.

Steps to be taken to ensure the accuracy and reliability of data include the selection of qualified investigators and appropriate study centers; review of protocol procedures with the investigator and associated personnel before the study and periodic monitoring visits by the sponsor. Written instructions will be provided for administration and collection of study questionnaires.

Guidelines for CRF completion will be provided and reviewed with study personnel before the start of the study. The sponsor will review CRFs and patient questionnaires for accuracy and completeness after transmission to the sponsor; any discrepancies will be resolved with the investigator or designee, as appropriate. After upload of the data into the clinical study database they will be verified for accuracy and consistency with the data sources.

3.4 *Data Management and Storage Process*

3.4.1 *Data Management*

Data management and data quality check will be performed to remove errors and inconsistencies in order to assure the appropriateness of the study data set to assess the study objectives. Data entry screens will be developed and tested prior to initiating

data collection to reduce data entry errors. If required, IMS will provide AbbVie with data for analysis.

Each site coordinator will be instructed to answer patients' queries which may arise in relation to the questionnaires and check the patients' input to make sure all questions are answered.

3.4.2 Storage Process

Following data quality checks, each dataset will be converted to SAS and merged for analysis. All information included in the CRF and the patients' questionnaires will be checked in order to detect possible queries to solve and will be extracted to a specifically designed database, where it will be validated by IMS personnel to ensure its quality. Finally, data analysis will be conducted and final results reported.

The databases will be stored in IMS data servers. Data servers are submitted to daily backups in order to increase the security on all data managed in the collection process.

All paper based questionnaires will be stored in a secured, locked area for a period of 7 years, after which all data will be shred using an agency specialized in disposal of confidential documents.

3.5 Definitions of Study Variables

The key variables of interest in this study are demographic and clinical characteristics, patient-reported health and disability outcomes, and healthcare resource utilizations. Most variables will be measured at baseline (i.e. index), and at weeks 12 and 24 after the initiation of Adalimumab; healthcare resource utilization will be summarized over the 6 month post-index period.

3.5.1 *Outcome/Endpoint Variables - Scoring of PRO Questionnaires*

Health Assessment Questionnaire Disability Index (HAQ DI)

In the HAQ DI, each category contains four response options ranging from 0-3, where 0 = without any difficulty and 3 = unable to do. In any event, a patient must have a score for at least six of the eight categories (i.e. Dressing and grooming, arising,

eating, walking, hygiene, reach, grip, and activities). The HAQ DI's scoring conventions allow for the computation of two disability indices:

1. Standard HAQ DI (preferred and traditional scoring method; takes into account the use of aids/devices)

There are three steps:

- 1) Sum the 8 category scores by using the highest sub-category score from each category.
 - For example, there are three sub-category items in "Eating". A patient responds with a 1, 2, and 0, respectively; thus, the category score is 2.
- 2) Adjust for use of aids/devices and/or help from another person when indicated.
 - Adjust the score for a category by increasing a 0 or 1 to a 2.
 - If the patient's highest score is a 2, it would remain as 2.
- 3) Divide the summed category scores by the number of categories answered to obtain a HAQ DI score of 0-3 (3=worst functioning).

2. Alternative HAQ DI Score (without aids/devices)

There are two steps:

- 1) Sum the scores for each category, ignoring scoring for aids/devices
- 2) Divide by the number of categories answered (minimum 6 required). This yields a score of 0-3 (3=worst functioning).

Short Form (36) Health Survey (SF-36)

SF-36 scoring will be conducted by following these 7 steps in accordance to the developer's recommendations:

Step 1: Data entry

SF-36 scoring must ensure that the survey form is complete and the respondent's answers are unambiguous. If there are missing responses, using a scoring algorithm could derive scores across the eight SF-36 health domain scales for nearly all survey respondents. If there are multiple responses for a single item, the following rules are applied:

1. If a respondent marks two responses that are adjacent to each other, randomly pick one, and enter that number.
2. If a respondent marks two responses that are not adjacent to each other, consider that item missing.
3. If a respondent marks three or more responses, consider that item missing.

Alternatively, one can opt to treat all items with more than one response as missing.

Step 2: Recoding item response values

This is a process that derives the final item response values, or scores, to be used when calculating the raw scale scores for each health domain.

Step 3: Determining the health domain scale total raw scores

Following item recording, which includes resolving items with missing data, a total raw score is computed for each health domain scale. The total raw score is the simple algebraic sum of the final response values for all the values for all the items in a given scale. The simple scoring method is possible because all the items in a given scale have roughly equivalent relationships to the underlying health construct being measured and because no item is used on more than one scale. As a result, it is not necessary to standardize or weight items.

Step 4: Transforming health domain scale total raw scores to 0-100 scores

Health domain scale total raw scores are converted to 0-100 scores using the following formula:

$$\text{Transformed scale score} = \frac{(\text{Actual raw score} - \text{Lowest possible raw score})}{\text{Possible raw score range}} \times 100$$

Step 5: Transforming health domain scale 0-100 scores to T scores using health domain z scores

The advantages of standardizing the health domain scales and converting 0-100 scores to norm-based scores using a T-score transformation are that health domain scale results can be meaningfully compared with each other and that these scores have a direct interpretation in relation to the distribution of scores in the 2009 US general population.

The first step is to convert the 0-100 scores into a linear z-score. A z-score would ensure each health domain scale has a mean of 0 and a standard deviation of 1 in the 2009 US general population. A z-score is computed by subtracting each health domain scale's 2009 US general population mean from the 0-100 score for that scale, and dividing the difference by the given scale's standard deviation. Thus, the following formula is applied to convert 0-100 scores into z-scores:

$$\text{z-score} = \frac{([\text{0-100 score}] - [83.29094])}{(23.75883)}$$

Z-scores are then transformed into T-scores (mean = 50, SD = 10) using the following formula:

$$T\text{-Score} = 50 + (z\text{-score} \times 10)$$

Step 6: Scoring the physical and mental component summary measures using health domain z scores

The Physical Component Summary (PCS) and Mental Component Summary (MCS) measures are then scored using a three-step procedure, regardless of whether a standard or acute form was administered. First, the eight health domain scales are standardized using means and standard deviations from the 2009 U.S. general population. Second, these standardized scores are aggregated using weights (factor score coefficients) from the 1990 US general population. Computation of an aggregate physical component score consists of multiplying each health domain scale z-score by its respective physical factor score coefficient and then summing the eight products. Similarly, an aggregate mental component score is obtained by multiplying each health domain scale z-score by its respective mental factor score coefficient and summing the eight products. To illustrate, a portion of the formula for aggregating scales when estimating a standard form of aggregate mental component score is as follows:

$$\begin{aligned} \text{Aggregate mental component score} = \\ (\text{PF z-score} \times -0.22999) \dots + (\text{MH z-score} \times 0.48581) \end{aligned}$$

Third, aggregate PCS and MCS scores are standardized using a linear T-score transformation with a mean of 50 and a standard deviation of 10. The formulas for computing the norm-based T score for each component summary measure are:

$$\begin{aligned} \text{PCS T-score} &= 50 + (\text{Aggregate physical component score} \times 10) \\ \text{MCS T-score} &= 50 + (\text{Aggregate mental component score} \times 10) \end{aligned}$$

Step 7: Scoring the response consistency index (RCI)

The Response Consistency Index (RCI) is optional, but is a simple and easy way to evaluate the consistency of responses to individual survey items. The RCI comprises of 15 pairs of items and assesses each pair for consistency. If a pair of responses is consistent, then the RCI score for that pair would be 0. Conversely, a pair of inconsistent responses would earn a score of 1. For example, if a respondent indicates that he or she can “walk more than a mile” but, at the same time, cannot “walk 100 yards,” then this item pair would be considered inconsistent and would earn 1 RCI point. For a given respondent, the final RCI score is the sum of the scores earned on the 15 consistency checks. Thus, the best (i.e., most consistent) RCI score is 0 and the worst (i.e., least consistent) score is 15. Note that it is not necessary for a respondent to have complete data for all 15 pairs to compute the RCI (pairs with missing or out-of-range data are not used in the final calculation). However, if all 15 pairs have missing data for one or both

items, then the RCI for that respondent cannot be scored.

EuroQol 5 dimension, 3 level quality of life questionnaire (EQ-5D-3L)

The EQ-5D-3L questionnaire is made up for two components; health state description and evaluation.

As to the health state description, the EQ-5D-3L descriptive system contains 5 categories (mobility, self-care, usual activities, pain/discomfort, and anxiety/depression). Each category contains three responses choices: top (having no problems), middle (having some or moderate problems), and bottom (being unable to do/having extreme problems). The top response choice is coded as “1”, the middle response choice as “2”, and the bottom response choice as “3”; while ambiguous values (e.g. multiple boxes ticked for one category) are treated as missing values, which are coded as “9”. As a result, a person's health status can be defined by a 5-digit number, ranging from 11111 (having no problems in all dimensions) to 33333 (having extreme problems in all dimensions). For example, 12321 indicates having no problems in mobility and anxiety/depression, having slight problems in self-care and pain/discomfort, and having extreme problems in usual activities. Thus, there are potentially 243 ($=3^5$) different health states.

Visual analogue scale (VAS) is the second part of the questionnaire, asking to mark health status on the day of the interview on a 20 cm vertical scale with end points of 0 and 100. There are notes at the both ends of the scale that the bottom rate (0) corresponds to “the worst health you can imagine”, and the highest rate (100) corresponds to “the best health you can imagine”. The respondents have to draw a line from the box on the questionnaire to the scale indicates the health state of the interviewed day; while ambiguous values (e.g. the line crosses the VAS twice) should be treated as missing values, which are coded as “999”. Eventually, the EQ-5D-3L results can be converted into a single index value; many different terms are in use for these index values, such as preference weights, preference-based values, utilities, QALY weights, etc.

Work Productivity and Activity Impairment (WPAI)

WPAI outcomes are expressed as impairment percentages, with higher numbers indicating greater impairment and less productivity (i.e., worse outcomes) as follows:

Questions

Q1 = currently employed

Q2 = hours missed due to specified problem

Q3 = hours missed other reasons

Q4 = hours actually worked

Q5 = degree problem affected productivity while working

Q6 = degree problem affected regular activities

Scores

Multiply scores by 100 to express in percentages.

- Percent work time missed due to problem

$$Q2 / (Q2+Q4)$$

- Percent impairment while working due to problem

$$Q5 / 10$$

- Percent overall work impairment due to problem

$$Q2/(Q2+Q4)+[(1-Q2/(Q2+Q4) \times (Q5/10)]$$

- Percent activity impairment due to problem

$$Q6 / 10$$

Patient Treatment Satisfaction Questions

The patient treatment satisfaction questions were developed de novo for this study and are not considered “validated” questions. There are totally 4 questions asking about the patients’ satisfaction with the following 4 aspects respectively:

1. The way RA treatment improves the morning stiffness in and around the joints.
2. The way RA treatment improves the mobility.
3. The way RA treatment improves the ability to perform daily living requiring fine motor skills.
4. The overall RA treatment.

There are totally 5 responses for each of the question: very satisfied, somewhat satisfied, neither satisfied nor dissatisfied, somewhat dissatisfied, and very dissatisfied.

3.5.2 *Exposure/Independent Variables of Interest*

- **Patient demographics (if data available)**
 - Date of birth
 - Age at baseline
 - Age groups
 - Gender at birth
 - Marital status (married, unmarried)
 - Medical plan type
 - ✓ The type of healthcare plan each patient is enrolled in at baseline will be determined, including National/Public insurance, Private insurance, Employer benefits, and Other
- **Clinical characteristics**
 - Initial Diagnosis of Rheumatoid Arthritis (RA)
 - ✓ Year of initial diagnose
 - Initiation of Adalimumab
 - ✓ First time administration (DD/MM/YYYY)
 - ✓ Dosage of first injection (in mg)
 - Disease status of RA
 - ✓ Moderate (defined as Disease Activity Score in 28 Joints (DAS28) between 3.2 and 5.1)
 - ✓ Severe (DAS28>5.1)
 - Erythrocyte sedimentation rate (ESR) (in mm/hour)
 - C reactive protein (CRP) (in mg/L)
 - Disease Activity Score in 28 joints (DAS28)

To calculate the DAS28, the physician or specialist nurse will:

1. Count the number of swollen joints (out of the 28)
2. Count the number of tender joints (out of the 28)
3. Take blood to measure the erythrocyte sedimentation rate (ESR) or C reactive protein (CRP); the latest measurement in the medical records may also be used if a blood draw is not standard for that visit

4. Ask the patient to make a 'global assessment of health' which will be indicated by marking a 10 cm line between very good and very bad

The physician or specialist nurse will then mark each component score on the CRF and the DAS28 score if calculated (an online scoring calculator for the DAS28 can be found at <http://www.das-score.nl/das28/DAScalculators/dascalculators.html>).

The DAS28 will be scored using the following formula:

$$\text{DAS28} = 0.56 * \text{sqrt}(\text{tender28}) + 0.28 * \text{sqrt}(\text{swollen28}) + 0.70 * \ln(\text{ESR or CRP}) + 0.014 * (\text{Global assessment of Health})$$

DAS28 scores will be interpreted using the following categorization:

- ✓ Remission: DAS28 \leq 2.6
- ✓ Low Disease Activity: $2.6 < \text{DAS28} \leq 3.2$
- ✓ Moderate Disease Activity: $3.2 < \text{DAS28} \leq 5.1$
- ✓ High Disease Activity: DAS28 > 5.1

– comorbidities

- ✓ Myocardial infarction
- ✓ Congestive heart failure
- ✓ Peripheral vascular disease
- ✓ Cerebrovascular disease
- ✓ Dementia
- ✓ Chronic pulmonary disease
- ✓ Connective tissue disease
- ✓ Ulcer disease
- ✓ Mild liver disease
- ✓ Diabetes
- ✓ Hemiplegia
- ✓ Moderate or severe renal disease
- ✓ Diabetes with end-organ damage
- ✓ Any tumor
- ✓ Leukemia
- ✓ Lymphoma
- ✓ Moderate or severe liver disease
- ✓ Metastatic solid tumor
- ✓ AIDS

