9.2.4.7 Study Documents

Clinical case report form (CRF)

The clinical CRF will document the patient's current status (moderate, severe RA), Disease Activity Score in 28 joints (DAS28), prior and current treatments and other relevant clinical and demographic data to be used in segmenting the population during analysis.

To calculate the DAS28 the physician or specialist nurse will:

1. Count the number of swollen joints (out of the 28)
2. Count the number of tender joints (out of the 28)
3. Record the blood test data of erythrocyte sedimentation rate (ESR) or C reactive protein (CRP) using the latest measurement in the medical records
4. Record the 'global assessment of health' of patients, which will be indicated by marking a 10 cm line between very good and very bad

The physician or specialist nurse will then mark each component score on the CRF and the DAS28 score if calculated (an online scoring calculator for the DAS28 can be found at [REDACTED])

The DAS28 will be scored using the following formula:

$$\text{DAS28 ESR} = 0.56 * \text{sqrt}(\text{tender28}) + 0.28 * \text{sqrt}(\text{swollen28}) + 0.70 * \ln(\text{ESR}) + 0.014 * (\text{Global assessment of Health in cm})$$

$$\text{DAS28 CRP} = 0.56 * \text{sqrt}(\text{tender28}) + 0.28 * \text{sqrt}(\text{swollen28}) + 0.36 * \ln(\text{CRP}) + 0.014 * (\text{Global assessment of Health in cm}) + 0.96$$

DAS28 scores will be interpreted using the following categorization:

- Remission: $DAS28 \leq 2.6$
- Low Disease activity: $2.6 < DAS28 \leq 3.2$
- Moderate Disease Activity: $3.2 < DAS28 \leq 5.1$
- High Disease Activity: $DAS28 > 5.1$

The full CRF is presented in Appendix C.

PRO questionnaires

The following PRO questionnaires will be included in the patient questionnaire packet.

Health Assessment Questionnaire Disability Index (HAQ DI)

The HAQ DI is a patient-reported questionnaire to assess functioning impacted by RA. It includes the categories of dressing and grooming, arising, eating, walking, hygiene, reach, grip and common daily activities. It asks patients about the amount of difficulty they experience in these activities as well as the use of aids and/or devices. The HAQ also has a numeric rating scale (NRS) (13) to assess pain on a scale from 0 to 10. Self-administered by the patient, the completion time is approximately 3-4 minutes. The full version of HAQ DI is presented in Appendix D.

Short Form (36) Health Survey (SF-36)

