Appendix C. Clinical Case Report Form (CRF)

Baseline:

1023259 Real-World Impact of RA
[Site number] - [Participant ID]

Clinician Case Report Form (Baseline)

All of the following information must be completed by the clinician or his/her representative.

Clinician name: _____

Clinician signature: _____

Patient ID	[Site #]	-	[Participant #]		
Today's date	[Day]	/	[Month]	/	[Year]

Please provide the information below.	
1. When was the patient diagnosed with Rheumatoid Arthritis?	[Year]
2. What is the patient's current disease status?	 Moderate  Severe

1023259 Real-World Impact of RA
 -
Site number Participant ID

Please provide the information below.		
3. Please perform a swollen and tender joint examination on your patient using the figure below and record the total number of tender/swollen joints in the appropriate boxes on the right.	 Tender Joint Count	 Swollen Joint Count
If diagnosis is RA:		
4. Please record the most recent Erythrocyte Sedimentation Rate (ESR) (in mm/hour) or C-reactive protein (CRP) (in mg/L) of this patient.	 ESR (mm/hour) Test Date (DD/MM/YYYY): ____/____/_____  CRP (mg/L) Test Date (DD/MM/YYYY): ____/____/_____ 5. Please record the latest DAS28 score*, if calculated	

* For calculation instruction, please refer to study protocol, page 21, clinical case report form (CRF).

1023259 Real-World Impact of RA
[REDACTED]
[REDACTED]
Site number - Participant ID

6. Please check all the comorbidities this patient has currently.

- ₀ No comorbidity
- ₁ Myocardial infarction
- ₂ Congestive heart failure
- ₃ Peripheral vascular disease
- ₄ Cerebrovascular disease
- ₅ Dementia
- ₆ Chronic pulmonary disease
- ₇ Connective tissue disease
- ₈ Ulcer disease
- ₉ Mild liver disease
- ₁₀ Diabetes
- ₁₁ Hemiplegia
- ₁₂ Moderate or severe renal disease
- ₁₃ Diabetes with end-organ damage
- ₁₄ Any tumor
- ₁₅ Leukemia
- ₁₆ Lymphoma
- ₁₇ Moderate or severe liver disease
- ₁₈ Metastatic solid tumor
- ₁₉ AIDS

1023259 Real-World Impact of RA
[REDACTED]
Site number - Participant ID

7. Please check all the prior medications this patient has received for her/his Rheumatoid Arthritis in the last 6 months.
(No response option for biologics is given as the current study recruits only patients with no history of any biologics prior to the study).

Drug Name	Average number of pills per day	Dose strength	Times per month

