All of the following information must be completed by the clinician or his/her representative.

Clinician name: _____

Clinician signature: _____

[figure not shown]
[figure not shown]
Site & participant ID

Today's date: / /

Please provide the information below.		
1. What is the patient's current disease status?	 Moderate	 Severe

1023259 Real-World Impact of RA

100

Please provide the information below.
 
2. Please perform a swollen and tender joint examination on your patient using the figure below and record the total number of tender/swollen joints in the appropriate boxes on the right.
		 	Tender Joint Count	 	Swollen Joint Count

If diagnosis is RA:
 
 
  
 
  
 
					

3. Please record the most recent Erythrocyte Sedimentation Rate (ESR) (in mm/hour) or C-reactive protein (CRP) (in mg/L) of this patient.
			
   ESR (mm/hour)
 
   CRP (mg/L)
		

4. Please record the latest DAS28 score*, if calculated
					

* For calculation instruction, please refer to study protocol, page 21, clinical case report form (CRF).

1023259 Real-World Impact of RA
[Site number] - [Participant ID]

[figure not shown]
5. Please check all the surgeries this patient has received for her/his Rheumatoid Arthritis since the last completed survey.			
 No surgery performed			
 Yes →	Type of Surgery (Please input the number of the list below)	Length of Stay*	Date of surgery (DD/MM/YYYY)
	 1 _____	_____ days	_____/_____/_____
	 2 _____	_____ days	_____/_____/_____
	 3 _____	_____ days	_____/_____/_____
	 4 _____	_____ days	_____/_____/_____
	 5 _____	_____ days	_____/_____/_____
List of common surgeries for rheumatoid arthritis:			

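### The SAP scores DAS28 with one formula for ESR or CRP; the protocol has a separate CRP formula, so any CRP-based score computed by the SAP formula is shifted by 0.34 × ln(CRP) − 0.96

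*SAP*

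**What the plan says.** SAP 3.5.2, under clinical characteristics, gives a single scoring formula for DAS28. After the two joint-count terms it reads "0.70 * \ln(\text{ESR or CRP}) + 0.014 * (\text{Global assessment of Health" and has no added constant. Protocol 9.2.4.7 gives two formulas. The ESR version has weight 0.70 on ln(ESR) and no constant. The CRP version ends "0.36 * \ln(\text{CRP}) + 0.014 * (\text{Global assessment of Health in cm}) + 0.96". The joint-count weights (0.56 and 0.28), the global-assessment weight (0.014) and the activity cut-offs (2.6, 3.2, 5.1) are the same in both documents.

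On who produces the score, SAP 3.5.2 says: "The physician or specialist nurse will then mark each component score on the CRF and the DAS28 score if calculated". The clinical forms in Protocol Appendix C ask: "Please record the latest DAS28 score*, if calculated". Their footnote is "For calculation instruction, please refer to study protocol, page 21, clinical case report form (CRF". Either marker may be supplied: "Please record the most recent Erythrocyte Sedimentation Rate (ESR) (in mm/hour) or C-reactive protein (CRP) (in mg/L) of this patient".

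The SAP uses DAS28 for the baseline summary and activity categories (5.2) and for the regressions of patient-reported outcomes on DAS28, and of their changes on change in DAS28 (5.5, Tables 10.1 and 10.2). Baseline disease severity also enters the sensitivity ANOVA (5.3) and Table 11 (5.5). SAP 3.5.2 defines severity by the score, "Moderate (defined as Disease Activity Score in 28 Joints (DAS28) between 3.2 and 5.1" for the moderate class, while the form also has a clinician tick-box for "current disease status".

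**The concern.** Protocol 9.7.1 makes the approved analysis plan binding for all analyses, and nothing else in the SAP corrects the formula. An analyst who follows it gives CRP the ESR weight and leaves out the constant. The SAP's own eligibility criterion names DAS28 (ESR) and DAS28 (CRP) as two scores, yet its scoring section supplies only one formula.

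There is a realistic route to using it. The site-entered score is optional. Where it is blank, the analyst either leaves DAS28 missing, since SAP 3.5.5 allows no imputation for this variable, or computes it. The only formula in the SAP is the combined one. One DAS28 variable could then hold scores on two scales.

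At stake are the baseline activity categories and the predictors in Tables 10.1 and 10.2. In Table 10.2 the distortion depends on how much CRP changes, so it would alter the slopes and not merely move the intercept.

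**Working it through.** **Inputs.**
- SAP 3.5.2: marker term 0.70 × ln(ESR or CRP), constant 0.
- Protocol 9.2.4.7, ESR: 0.70 × ln(ESR), constant 0.
- Protocol 9.2.4.7, CRP: 0.36 × ln(CRP), constant 0.96.
- CRP in mg/L (SAP 3.5.2 and the Appendix C forms).
- Assumptions: the CRP values and joint counts below are illustrative, and the global assessment is in the same unit under both formulas.

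The plan states no figure for this point, so there is none to reproduce.

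**Step 1: difference in a single score.** The joint-count and global-assessment terms cancel.
- ESR: 0.70 × ln(ESR) − 0.70 × ln(ESR) = 0.
- CRP: SAP minus protocol = (0.70 − 0.36) × ln(CRP) − 0.96 = 0.34 × ln(CRP) − 0.96.
- Zero at CRP = exp(0.96 / 0.34) = 16.8 mg/L; negative below, positive above.

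| CRP (mg/L) | SAP minus protocol |
|---|---|
| 1 | −0.96 |
| 3 | −0.59 |
| 5 | −0.41 |
| 10 | −0.18 |
| 16.8 | 0 |
| 50 | +0.37 |

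Computing both formulas in full over a grid of joint counts and global assessments gave the same differences throughout.

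**Step 2: effect on categories.**
- Protocol 3.50 at CRP 3: 3.50 − 0.59 = 2.91. Moderate becomes low.
- Protocol 5.00 at CRP 50: 5.00 + 0.37 = 5.37. Moderate becomes high.
- From components (6 tender, 5 swollen, CRP 5, global 5 cm):
  - Protocol: 0.56√6 + 0.28√5 + 0.36 ln 5 + 0.014 × 5 + 0.96 = 3.61, moderate.
  - SAP: 0.56√6 + 0.28√5 + 0.70 ln 5 + 0.014 × 5 = 3.19, low.

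**Step 3: effect on change scores, CRP at both visits.** The constant cancels, and the CRP part of the change is multiplied by 0.70 / 0.36 = 1.94. For a fall from 20 to 2 mg/L:
- Protocol: 0.36 × ln(0.1) = −0.83.
- SAP: 0.70 × ln(0.1) = −1.61.

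**Step 4: which analyses read the score.**
- Directly: the baseline DAS28 summary and categories (SAP 5.2), and Tables 10.1 and 10.2 (SAP 5.5).
- Only if severity is taken from the computed score: the sensitivity ANOVA (SAP 5.3) and Table 11 (SAP 5.5).
- Not at all: the primary paired t-test on HAQ DI, the secondary tests and the sample size.

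**The case against.** The strongest reply is that the SAP formula may never be run. It follows a list of steps for the physician or nurse, so it can be read as a description of site scoring. DAS28 is not among the derived variables in SAP 3.5.4. The forms send sites to the protocol for the calculation, and both documents also point to an online calculator. If the analysis takes the site-entered score, the SAP formula need not enter the results at all. This stands as a limit on the consequence. It does not remove the conflict: the SAP states the formula as the scoring rule, the site score is optional, and no sentence says which score is analysed.

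It is also fair that the numerical examples rest on chosen CRP values and that the documents do not give the share of patients scored by CRP. The size of any effect on the tables cannot be computed.

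Two stronger readings should be resisted. A reader might infer that the planned DAS28 results will be wrong; the documents show only that they could be. A reader might also infer that the SAP formula can label an eligible patient as in remission only when CRP is below exp(0.36 / 0.34) = 2.88 mg/L. That holds only for patients eligible by the protocol's DAS28 (CRP), because eligibility may instead be met on DAS28 (ESR). With 3 tender and 2 swollen joints, global assessment 5 cm, ESR 25 and CRP 5, the protocol's DAS28 (ESR) is 3.69 (eligible), its DAS28 (CRP) is 2.98, and the SAP formula with CRP gives 2.56, which is remission.

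The missing unit label in the SAP formula, the comparability of ESR- and CRP-based scores when the marker changes between visits, and the choice between tick-box and score for baseline severity are separate matters. This point does not depend on them.

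**Conclusion.** The conflict is certain from the text: the two documents score CRP-based DAS28 differently. For a single score the discrepancy is 0.34 × ln(CRP) − 0.96, which runs from −0.96 at 1 mg/L to +0.37 at 50 mg/L and is enough to move patients across an activity cut-off. For changes with CRP at both visits it multiplies the CRP component by 1.94. These figures assume a common unit for the global assessment.

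The consequence is conditional. It needs DAS28 to be computed by the SAP formula, and it touches only CRP-based scores. The exposure is one baseline description and two exploratory tables, with the sensitivity ANOVA and Table 11 exposed only if severity comes from the computed score. This should be fixed before analysis because the rule is wrong as written and cheap to correct, but it does not threaten the main result.

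**What to change.** In SAP 3.5.2:

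1. Replace the single formula with the protocol's separate ESR and CRP formulas. The protocol version is the one to carry over: the forms direct sites to it, and the eligibility text in both documents treats DAS28 (ESR) and DAS28 (CRP) as distinct scores.
2. State whether the site-entered or a recomputed DAS28 is analysed, and which marker is used when both are recorded; the baseline form has boxes for both.
3. Do not mix protocol-scored and SAP-formula scores in one variable.

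The cost is an SAP text edit and minor programming. No patient is dropped and no analysis is added. If recomputation is chosen, first confirm that the global assessment was captured: the forms as reproduced show no field for it, though some of their figures are missing. If site-entered scores are chosen, blank entries stay missing under SAP 3.5.5 and should be counted in the report.
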